PROTOCOL TITLE: Gabapentin for pain control after osmotic dilator insertion and prior to D&E procedure: a randomized controlled trial

1) Protocol Title

Title: Gabapentin for pain control after osmotic dilator insertion and prior to D&E procedure: a randomized controlled trial

Protocol Version Date: 01/11/2018

2) Objectives

Pain management in the context of abortion is a topic that is both challenging and necessary to research. The Society of Family Planning (SFP 2014) lists it as a top research priority. Most research to date has focused on pain during the abortion procedure. One area that remains under investigated is women's pain experience during the time osmotic dilators are in the cervix prior to the dilation and evacuation procedure. As a result, management of pain during this time period varies greatly and is largely based on anecdotal experience. Adjunctive pain management with non-narcotic medications such as gabapentin may have a place during this time. Gabapentin is unique in that it is both well tolerated with minimal contraindications and low cost with 600 mg doses as low as \$0.24. Additionally, widespread dissemination of cell phones and text messaging now gives us the opportunity to communicate with women about their dilator-related pain experience in real-time, potentially improving data quality.

We have planned a randomized, controlled trial of repeated doses of gabapentin compared to placebo for pain management during the time after dilator insertion and prior to D&E the subsequent day. Participants will receive gabapentin 600 mg or placebo prior to dilator insertion. Pain scores will be measured via numeric rating scale (NRS) at baseline and 5 minutes after insertion while the participant is in clinic. Additional pain scores as well as side effect and additional analgesic use will be obtained by text message while the patient is at home at 2 hours, 4 hours, and 8 hours after time of dilator insertion. Final pain score, side effect, and analgesic use assessment will occur upon presentation to the pre-operative area for D&E. We hypothesize that women who receive gabapentin beginning at the time of dilator placement for a D&E procedure will report a smaller increase in pain from baseline at 8 hours after dilator placement compared to women receiving placebo.

3) Background

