3. Participant will be asked to provide pain level on 11-point (0-10) NRS immediately before study drug ingestion as the baseline pain score. Baseline symptoms (sedation and dizziness) will also be recorded.
4. Women will ingest the assigned gabapentin 600 mg or placebo
 - a. Stratified block randomization will occur to achieve even distribution of women based on vaginal parity (no prior vaginal delivery versus one or more prior vaginal deliveries). This strategy will ensure similar numbers of women with vaginal parity between gabapentin and placebo groups as this may be an important factor influencing pain with dilators in general.
 - b. A UC Davis Investigational Drug Services (IDS) pharmacist will use computer-generated randomization to place active or placebo treatment in two groups of sequentially numbered vials (to account for block randomization based on parity)
5. The physician will proceed with dilator insertion via our existing standardized method (including standard cervical anesthesia with 1% xylocaine 20 mL, standard number of dilators based on gestational age). Number of dilators and any pharmacologic means of cervical preparation are already reported in a standardized template and will be available for chart review.
6. Post-dilator pain will be assessed via NRS at five minutes after dilator insertion. Additional symptoms (sedation and dizziness) will be recorded.
7. Women will be discharged home with:
 - a. One additional study medication (Gabapentin 600 mg or placebo) to take at home 8 hours after the initial dose. This medication will be labeled by the IDS and completed by administering physician.
 - b. Standard prescriptions for acetaminophen 300 mg/codeine 30 mg and ibuprofen 800 mg to take as needed.
 - c. A reminder form that includes 24-hour research contact information, the times when they can expect text messages, a reminder to take the home dose of their assigned study medication at 8 hours after dilator insertion (exact time will be written out) and a reminder to bring the empty study medication bottle with them when they present for their procedure the next day.
 - d. Recommendation that they have a ride to and from abortion procedure the subsequent day.
8. Participants will be sent a baseline text message from the study phone prior to leaving the clinic. Participants will be encouraged to enable privacy features on their personal phone. Examples of security features will be reviewed and included in the consent.

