9. Participants will be contacted via text message at 2, 4, and 8 hours after dilator insertion.
 - a. Text messages will originate from a password protected study cell phone. Android application "SMS scheduler" will be used to send standardized text messages to the participant at pre-programed time intervals from time of dilator insertion.
 - b. Text message content:
 - i. Current NRS pain score
 - ii. Inventory of analgesic use since last contact
 - iii. Presence of symptoms (sedation and dizziness)

PROTOCOL TITLE: Gabapentin for pain control after osmotic dilator insertion and prior to D&E procedure: a randomized controlled trial

- iv. Reminder to take the assigned study medication (at 8 hours only)
10. Upon admission to the pre-operative ward prior to D&E, we will document the time and assess the current NRS pain score, additional analgesic use since 8 hour text message contact, and presence of symptoms (sedation and dizziness)

Blinding

Participants and providers will be blinded to study drug allocation as all study drug will be prepared by the pharmacist and placed into numbered drug bottles.

Privacy protection

Participant privacy is another ethical concern in this study. Participants may have people with access to their cell phones who do not know about the pregnancy or abortion. Compromising a woman's privacy about this matter could put her at risk depending on her life situation. To prevent this, I plan to use generic language that does not identify the context of the woman's care. Women will be counseled regarding their ability to rescind their participation at any point. Below is the verbatim content of each text message that will be sent to participants. These text messages will be sent in order, with a programmed one-minute interval between each question:

1. "What is your current pain level on a scale of 0-10? (Zero is no pain and ten is the worst pain imaginable)"
2. "How many pills of ibuprofen have you taken since the last text?"
3. "How many pills of acetaminophen with codeine have you taken since the last text?"
4. "Do you feel more dizzy than usual?"
5. "Do you feel more tired than usual?"

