reviewed. Physician investigators will assess for causality or relatedness of the adverse experience to the study.

- In accordance with UC Davis institutional review board (IRB) reporting policy, AEs will be reported at annual IRB renewal submission. SAEs that are unanticipated and thought to be related to the study (thereby placing research subjects at higher risk of harm than originally thought) will be reported to the IRB by the principal investigator within five days of becoming aware of the event.
- The study will be reviewed semimonthly at the Family Planning division research meeting, which includes all research staff. Any concerns regarding individual or trends in AEs will prompt further review of the study and consideration of study termination.
- Study allocation will remain concealed except in a scenario in which revealing allocation is clinically important for the participant's management

11) Withdrawal of Subjects

Based on the safety of existing research on both gabapentin for peri-procedure pain and an existing abortion-related study using text messaging of subjects, we do not anticipate frequent circumstances for participant withdrawal. There are both investigator and participant-initiated modes for subject withdrawal. Participants will be withdrawn from the study pending investigator review of AE that warrants removal or any SAE (see Section 10). Participants will be counseled at enrollment about how to withdrawal themselves from the study for any reason. If a participant is withdrawn from the study, no further data will be collected. We will inquire about the reason for withdrawal so we can monitor for AE/SAE.

12) Risks to Subjects

There are two primary categories of risk in this study:

1. *Study medication risk (Gabapentin):*

As noted in Section 7, Gabapentin is a safe, well tolerated medication that is an established agent of interest for peri-procedure analgesia. Contraindications and medication interactions are few. This study will be monitoring for the more common side effects that can happen (though not frequently in prior studies), including increased self-reported sedation and dizziness from baseline.[25]

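### Section 11 stops all data collection after any withdrawal, so a woman withdrawn by the investigator loses outcome assessments she has not refused (very small effect, cheap fix)

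*Combined protocol and SAP*

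**What the plan says.** Section 11 (Withdrawal of Subjects) states: "There are both investigator and participant-initiated modes for subject withdrawal". For the investigator's route it says: "Participants will be withdrawn from the study pending investigator review of AE that warrants removal or any SAE (see Section 10"). One unqualified data rule follows: "If a participant is withdrawn from the study, no further data will be collected". The section adds: "We will inquire about the reason for withdrawal so we can monitor for AE/SAE". On frequency, it says that "we do not anticipate frequent circumstances for participant withdrawal"; no rate is given.

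The assessments at stake are in Section 7: a pain score and symptoms 5 minutes after insertion, then texts at 2, 4 and 8 hours on pain, analgesic use and symptoms, and the same items on arrival for the procedure. The hypothesis in Section 2 concerns 8 hours: women given gabapentin "will report a smaller increase in pain from baseline at 8 hours after dilator placement compared to women receiving placebo". The home capsule is described as "One additional study medication (Gabapentin 600 mg or placebo) to take at home 8 hours after the initial dose", and the 8-hour text carries the reminder for it. The pre-operative assessment is therefore the only one scheduled clearly after the home dose.

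**The concern.** A woman's own wish to stop must end data collection, and the privacy part of Section 12 already lets her leave and have the texts stopped. An investigator's decision about an adverse event is not a refusal by the woman. Section 11 has only one state, being withdrawn from the study, and attaches the same data stop to both routes.

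Outcome data that may be obtainable are then discarded by rule, and the discarding is triggered by an event after randomisation. If such withdrawals differed between arms, the women analysed would no longer be the full randomised groups. Nothing else in the plan covers this loss. The allowance of up to 20% in Section 8 is for women who do not answer texts, and the Statistical Analysis text names a non-parametric test without an analysis set or a rule for missing scores.

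**Working it through.** **1. The passages side by side.** The plan gives no figure on this point, so the first check is one of reading. The passive wording of the data rule matches the sentence on investigator withdrawal, so that route is covered whether the rule is read narrowly or broadly. Section 10 continues adverse event logging, medical management, source review, causality assessment and reporting to the review board. Section 11 continues the question about the reason. None of these provides for the scheduled pain, analgesic and symptom assessments.

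**2. What is lost, by time of withdrawal.** Five assessments follow the clinic dose (5 minutes, 2 h, 4 h, 8 h, pre-operative).

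| Withdrawn | Assessments lost | 8-hour score lost? |
|---|---|---|
| After the clinic visit, before 2 h | 4 of 5 | Yes |
| Between 2 and 4 h | 3 of 5 | Yes |
| Between 4 and 8 h | 2 of 5 | Yes |
| After the 8-hour text | 1 of 5 | No |

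**3. Share of the sample.** The documents give no withdrawal rate, so 1 to 3 women is an assumption. 1/121 = 0.8% and 3/121 = 2.5%. The target of 121 is already more than twice the 58 that Section 8 derives with its non-response allowance (2 × 58 = 116), so power is not the issue.

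**4. Possible shift in the arm difference.** Assumptions: about 60 women per arm; no true effect; each arm holds the same small number of women who score 2 to 3 points higher than the rest; the losses fall on these women, before 8 hours. No document supports the 2 to 3 point gap or any imbalance. An arm that loses all its higher-scoring women has the mean of the rest. The other arm sits above that by (higher-scoring women still present ÷ women still present) × gap.

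- 1 lost versus 0: 1/60 × (2 to 3) = 0.033 to 0.050 points
- 3 lost versus 1: 2/59 × (2 to 3) = 0.068 to 0.102 points
- 3 lost versus 0: 3/60 × (2 to 3) = 0.10 to 0.15 points

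The arm that lost more women looks better by that amount. Divided by the 2-point difference in Section 8, these are 1.7–2.5%, 3.4–5.1% and 5.0–7.5%.

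**5. False-positive rate.** This was simulated with 6,000 runs per setting: 60 per arm, 20% random non-response, integer scores from 0 to 10 with mean 5.2, and SD 1.2 (the plan's value for a single score) or 2.5 or 3.0 (assumed). The test was a two-sided 5% Mann-Whitney test, also an assumption, because the plan says only that testing is non-parametric. Rejection was 4.6–5.1% with nobody withdrawn, 4.4–5.1% for 1 versus 0, 4.8–5.3% for 3 versus 1, and 4.7–6.0% for 3 versus 0 (simulation error about 0.3 percentage points). A smaller repeat of 3,000 runs reached 6.5% at 3 versus 0. There is little change except, at most, a slight rise in the most one-sided case.

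**The case against.** The strongest case against is that the route to losing the 8-hour score is very narrow. The adverse event must be one that warrants removal, or a serious one, and it must be recognised and acted on within about 8 hours. The wording on pending review can mean withdrawn while review is awaited, or only after review. On the second reading the event, its review and the withdrawal must all fall inside that window. After a serious event (hospitalisation, disability, threat to life or death), a comparable pain score may not be obtainable at all. A full stop also has a protective rationale, since Section 10 counts a significant privacy breach as an adverse experience and continued texting could be unwelcome or unsafe.

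Most of this stands, and it limits the size of the point. It does not remove the point. The adverse event route does not require hospitalisation, so able and willing women are plausible there. The pre-operative assessment can be lost on either reading. The privacy case can be handled by an explicit exception.

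Two stronger readings are tempting, and the documents support neither. A reader might infer that safety follow-up also stops; Sections 10 and 11 show that it continues. A reader might infer that sedated or dizzy women would be removed, mostly from the gabapentin arm; those symptoms are scheduled outcomes, and nothing says that reporting them leads to withdrawal.

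**Conclusion.** The point holds as an avoidable loss created by the plan's own rule: a woman withdrawn by the investigator gives up assessments she has not refused. Its expected effect is very small, about 0.03 to 0.15 points. That range rests on assumed counts of 1 to 3 women, an assumed gap of 2 to 3 points, about 60 women per arm, and losses that all fall before 8 hours and unequally between arms. A reader might go further and infer that the primary comparison is biased. The documents do not support that: they expect few withdrawals, give no rate and show no difference between arms. This is a cheap improvement and not a threat to the trial's conclusion.

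**What to change.** In Section 11, limit the data stop to women who withdraw consent for data collection or ask for contact to end. Possible text:

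*Withdrawal by the investigator does not by itself end outcome assessment. The participant is asked to complete her remaining scheduled text and pre-operative assessments if she is able and does not decline. These data are analysed under her assigned arm. Who initiated the withdrawal, and when, is recorded. If she withdraws consent for data collection or asks for contact to stop, nothing further is collected beyond the reason, if she offers it, and required safety follow-up. Where the event concerns privacy or the safety of message contact, texts stop, and the pre-operative assessment is offered only if she agrees.*

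This says nothing about whether study drug stops, and it leaves the withdrawal criteria unchanged. The sponsor should state whether withdrawal comes before or after the investigator's review.

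The cost is one paragraph, and the contacts already exist: the scheduling application "will be used to send standardized text messages to the participant at pre-programed time intervals from time of dilator insertion", and the pre-operative interview is already planned. The downsides are a few extra contacts and a privacy check before texting continues, which may fall to on-call staff at night. The sponsor should also confirm that the payments tied to each contact apply. The consent pages are not in the text reviewed; if they repeat the rule, they need the same change. The protocol version is dated 01/11/2018 and Section 5 planned enrolment from February 2017 to January 2018, so on the planned dates the change may reach few women. Actual enrolment is not shown.
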